4.3.3. Subgroup Analyses of the Primary Outcomes

Subgroup analyses of mortality through 30 days (-2 days) and global response at Day 14 (± 1 day) will be performed to investigate the consistency of the treatment effects for different groups of subjects. Forest plots will be presented to visually assess the presence of treatment by subgroup interactions. All-cause mortality and global response at Day 14 (± 1 day) will be assessed separately within the following subgroups in the mITT population: sex (male versus

female), race (white versus non-white and Asian versus non-Asian), age category (<65 years versus ≥ 65 years), geographic region (United States/South America, Europe/Israel/Turkey, Asia-Pacific (excluding China/Taiwan), China/Taiwan), final diagnosis (candidemia only versus IC), and APACHE II score/ANC at Screening (APACHE II score ≥ 20 OR ANC < 500 cells/ μL versus APACHE II score < 20 AND ANC ≥ 500 cells/ μL), APACHE II score at Screening (≥ 20 , < 20, 10-19, < 10), ANC at Screening (< 500 cells/ μL versus ≥ 500 cells/ μL). All-cause mortality through 30 days (-2 days) and global response at Day 14 (± 1 day) will also be summarized in the subgroups defined by timing of the culture used to document the *Candida* infection (positive culture at randomization definitions 1 and 2). This subgroup will not be included in the Forest plots.

For each subgroup, the number and percentage of subjects alive and deceased at Day 30 and the number and percentage of subjects with a global cure, failure and indeterminate response at Day 14 (± 1 day) will be determined by treatment group. Two-sided 95% CIs for the observed difference in mortality rates and global cure rates will be calculated in the mITT population, using the unadjusted methodology of Miettinen and Nurminen.

4.3.4. Additional Efficacy Outcomes

Analyses for the additional efficacy endpoints will be performed using the mITT population.

Resolution of all systemic signs attributable at baseline to candidemia and/or invasive candidiasis for subjects receiving of Rezafungin for Injection and caspofungin at Day 5, Day 14 (± 1 day), Day 30 (-2 days) and Follow-up (Days 52-59) will be presented by treatment group. This analysis will be repeated for subjects additionally with mycological eradication.

All-cause mortality at Follow-up will be presented for the mITT population by treatment group using frequencies and percentage of subjects that were alive and deceased at Follow-up. In addition, Kaplan-Meier (KM) methods will be utilized to analyze survival time in the mITT and ITT populations. The probability of being alive at Day 5, Day 14, Day 30, and Day 55 will be determined by treatment group. In addition, the 25th, 50th (median), and 75th percentiles will be provided by treatment group. The number and percentage of subjects censored will be provided. KM survival curves will be provided. The number of subjects at risk and number died in each treatment group will be displayed below the x-axis at day= 0, 5, 14, 30, 55. Survival status will be provided in a by-subject listing.

The time to the first negative blood culture without subsequent positive culture from a sample drawn following the first dose of study drug will be summarized using KM methods for mITT population. The calculation will be in reference to the first dose date. For subjects who have negative blood culture prior to the first dose of study drug without subsequent positive culture, the time to the first negative blood culture will be set to zero. A log-rank test will be performed to test for differences in survival curves between treatment groups. Subjects will be censored if they receive an alternative antifungal (i.e., other than study drug) for the treatment of the candidemia, died or were lost to follow up prior to having the negative blood culture (see Section 2.3.3). KM survival curves will be provided. The 25th, 75th percentiles and the median survival time and 95% CIs will be determined by treatment group. This analysis will be repeated for the following subsets among the subjects with any post-baseline blood cultures: 1) Subjects with

positive culture at randomization definition 1 (defined in Section 2.8), 2) Subjects who did not receive systemic antifungal therapy prior to the first dose of study drug, 3) Subjects diagnosed with Candidemia only, and 4) Subjects diagnosed with Candidemia only with timing of positive culture at randomization definition 1 (defined in Section 2.8).

Results of blood culture, tissue/fluid culture from a normally sterile site, rapid diagnostic and radiological (and other imaging) testing will be provided in by-subject listings.

4.4. Analysis of Health Outcomes

The number and percentage of subjects admitted to the Intensive Care Unit (ICU) on or after Study Day 1 will be summarized by treatment group in the mITT population. For those subjects who did not die before hospital/ICU discharge, the time to discharge for each admission to hospital and to ICU will be generated and the longest length of stay for each subject will be summarized using descriptive statistics by treatment group in the mITT population. For subjects admitted to the hospital and to the ICU, the number of hospital/ICU admissions will be determined and the number and the percentage of the subjects with no ICU admission, 1 ICU admission, and 2 ICU admissions will be presented. In addition, for those subjects who did not die before hospital/ICU discharge, the total number of days in hospital, in ICU, and in general ward across all admissions will be determined. The total number of days in hospital is defined as the total number of days in hospital during the study period (i.e., if admission date is earlier than the first dose date, the number of days is defined as discharge date – first dose date +1; if admission date is on or later than first dose date, the number of days is defined as discharge date – admission date +1). The number of days from the initial admission and the one from re-admission (if applicable) will be summed to get the total number of days. For the subjects with missing hospital discharge date, the end of study date or the ICU discharge date, whichever is later, will be used for the discharge date. Descriptive statistics will be used to summarize the total number of days in hospital, in general ward, and for those admitted to the ICU, the total number of days in ICU, by treatment group in the mITT population. Similarly, the total number of days in hospital, in ICU, and in general ward at time of enrollment (defined as randomization date – admission date +1) will be summarized.

The number and percentage of subjects re-admitted to hospital and to ICU (re-admitted to ICU during initial hospitalization) after discharge by Day 30 (-2 days) and by Follow-up (Days 52-59) will be presented by treatment group for all subjects in the mITT population who were discharged from hospital, where the initial discharge date was on or after Study Day 1. Descriptive statistics will be used to summarize the time to first re-admission from the previous discharge date. The analysis will be repeated for re-admissions related to infectious disease and for re-admissions related to Candidiasis. Hospital admissions and re-admissions will be provided in by-subject listings

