10.3 Exploratory Outcomes

An exploratory efficacy outcome measure is resolution of attributable systemic signs of candidemia and/or invasive candidiasis that were present at baseline. These include fever, hypothermia, hypotension, tachycardia, tachypnea, and local signs of inflammation (i.e., erythema, edema, heat and pain at the site of the qualifying culture).

Health economics outcomes research (HEOR) variables are also exploratory outcomes. These include total length of hospital stay and length of ICU stay.

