13.6 Health Economics Outcome Research

Descriptive statistics of the total length of hospital stay and the total length of ICU stay will be provided by treatment group.

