2.4. Health Outcome Measures

For subjects admitted to the Intensive Care Unit (ICU) on or after Study Day 1, the number of ICU admissions, the time to discharge for each admission and the total length of stay in the ICU across all admissions will be summarized by treatment group. The number and percentage of subjects re-admitted after discharge by Day 30 (-2 days) and by Follow-up (Days 52-59) will be presented by treatment group in the mITT population for all re-admissions, for re-admissions related to infectious disease and again for re-admissions related to Candidiasis.

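### Hospital and ICU stay is summarised only in subjects who did not die before discharge, so the exploratory between-arm comparison can be biased in either direction if mortality differs

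*SAP*

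**What the plan says.** SAP 4.4 builds two stay measures, and both carry the same condition: "For those subjects who did not die before hospital/ICU discharge".

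- Longest stay: "For those subjects who did not die before hospital/ICU discharge, the time to discharge for each admission to hospital and to ICU will be generated". The result is then used as follows: "the longest length of stay for each subject will be summarized using descriptive statistics by treatment group in the mITT population".
- Total days: "for those subjects who did not die before hospital/ICU discharge, the total number of days in hospital, in ICU, and in general ward" are summed over admissions and summarised descriptively by arm.

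A missing hospital discharge date is replaced by the later of the end-of-study date and the ICU discharge date. The re-admission summaries in the same section are limited to mITT subjects "who were discharged from hospital, where the initial discharge date was on or after Study Day 1".

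The condition does not appear elsewhere. Protocol 13.6 says only "Descriptive statistics of the total length of hospital stay and the total length of ICU stay will be provided by treatment group". SAP 2.4, for subjects admitted to the ICU on or after Study Day 1, says that "the total length of stay in the ICU across all admissions will be summarized by treatment group". SAP section 6 nevertheless declares no differences from the protocol's analyses.

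On status, Protocol 10.3 states: "Health economics outcomes research (HEOR) variables are also exploratory outcomes". No confidence interval or test is planned for stay. Neither document plans a summary that combines death with stay, or an analysis of discharge with death as a competing event.

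**The concern.** The tables are presented by treatment group in the mITT population, and a reader will take them as a randomised comparison. They are not. Who remains depends on who died before discharge, and Day 30 mortality is the FDA primary outcome. If one drug prevents deaths, its arm keeps patients whose counterparts in the other arm have been removed. The two sets of survivors then differ in case mix, and the stay difference reflects that as well as any effect on stay.

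At stake is the reading of the health-economic tables. For a once-weekly drug compared with a daily infusion, length of stay is a result that people outside the trial are likely to pick up.

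**Working it through.** **Figures from the plan.** The documents state no figure for stay. The inputs used here are 20% Day 30 mortality per arm and 184 mITT subjects, 92 per arm (SAP 3.1). The sample size is consistent with its stated assumptions:

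- Global cure: 2 × 0.7 × 0.3 × (1.960 + 0.842)² / 0.2² = 82.4 per arm. With continuity correction, (82.4/4) × (1 + √(1 + 4/(82.4 × 0.2)))² = 92.1, against 92 stated.
- Mortality power at 92 per arm with a 1/n correction: Φ[(0.2 − 1/92)/√(2 × 0.2 × 0.8/92) − 1.960] = 89.4%, against 89.7% stated.

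**Subjects removed.** If every planned Day 30 death comes before discharge, 0.20 × 92 = 18.4 per arm, or 0.20 × 184 = 36.8 in all. Deaths after discharge would lower this count; in-hospital deaths after Day 30 would raise it.

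**Size of the shift.** Split each arm into three groups: 80% who survive to discharge on either drug and stay 20 days; a fraction (0.20 − m) who die on control but are rescued on treatment and stay L days; and a fraction m who die on either drug. The drug has no effect on the stay of the first group. Every stay length, and treatment mortality m of 15% or 10%, is an assumption and not in the documents.

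Survivor-only difference (treatment minus control) = [(0.20 − m)/(1 − m)] × (L − 20)

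- m = 0.15: factor 0.05/0.85 = 0.0588
- m = 0.10: factor 0.10/0.90 = 0.1111

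Days alive and out of hospital, zero credited after death, to horizon H: difference = (0.20 − m) × (H − L), or zero where L is at least H.

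| L, rescued patients' stay (days) | 15 | 20 | 30 | 40 | 55 |
|---|---|---|---|---|---|
| Survivor-only difference, m = 15% | −0.29 | 0 | +0.59 | +1.18 | +2.06 |
| Survivor-only difference, m = 10% | −0.56 | 0 | +1.11 | +2.22 | +3.89 |
| Days alive and out to Day 59, m = 15% | +2.20 | +1.95 | +1.45 | +0.95 | +0.20 |
| Days alive and out to Day 59, m = 10% | +4.40 | +3.90 | +2.90 | +1.90 | +0.40 |
| Days alive and out to Day 30, m = 15% | +0.75 | +0.50 | 0 | 0 | 0 |
| Days alive and out to Day 30, m = 10% | +1.50 | +1.00 | 0 | 0 | 0 |

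Three things follow.

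1. The sign of the survivor-only shift is the sign of L − 20. The condition alone does not fix it.
2. If m = 0.20 and the same patients die in each arm, the shift is zero.
3. Days alive and out of hospital never count against the drug that saves lives. To Day 30, however, it gives no credit for a rescued patient still in hospital at Day 30.

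**Adding deaths back is not a remedy.** If each death contributes an assumed 8 in-hospital days, the all-subject mean differs by (0.20 − m) × (L − 8). This runs from 0.05 × 7 = +0.35 to 0.10 × 47 = +4.70 days over the same grid, because early death shortens stay.

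**The case against.** The strongest reply is that little depends on these tables. They are exploratory and descriptive, and mortality is reported next to them: Day 30 mortality in SAP 4.3.1, and mortality at Follow-up with Kaplan-Meier survival in SAP 4.3.4. Summary tables show the number of subjects contributing (SAP 3.2), so a careful reader can see that deaths are missing. A shift of 0.6 day is also well inside noise: with about 74 and 78 survivors (0.80 × 92 and 0.85 × 92) and an assumed SD of 8 to 15 days, the standard error of the difference is SD × √(1/74 + 1/78), or 1.3 to 2.4 days. All of this stands and limits the importance of the point. It does not restore the randomised comparison, because separate mortality tables do not show how stay and death combine.

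It is also fair to say that days alive and out of hospital answers a different question from bed use. In the illustration its entire gain comes from the assumed mortality difference. That is a reason to keep the stay tables as well, under an accurate label.

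The mismatch with the protocol is small. Protocol 13.6 is one sentence and names no population, so the SAP may be read as adding detail. The wording still needs reconciling.

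A reader might infer that only subjects with a recorded live discharge remain. SAP 4.4 does not say that. It removes those who died before discharge; its rule for missing discharge dates can keep others in, and deaths after discharge stay in.

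**Conclusion.** The point holds as a minor one. SAP 4.4 conditions an exploratory comparison of stay on an outcome that treatment may affect, and nothing in either document offsets this. If mortality differs between arms, the bias can go either way. Under the assumed stays the shift runs from −0.3 to +2.1 days at 15% against 20% mortality, and from −0.6 to +3.9 days at 10% against 20%.

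A reader might infer that the rule necessarily makes a life-saving drug appear to lengthen stay. The documents do not support that. They give no link between severity and stay, they plan for 20% mortality in both arms, and the direction requires rescued patients to stay longer than other survivors. Nor do they support any effect on a primary or secondary conclusion, since stay is neither and is not tested.

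**What to change.** - In SAP 4.4, add days alive and out of hospital, and days alive and out of ICU, from Day 1 to Day 30 in all mITT subjects as the between-arm summary. Credit zero days after death, and treat unknown survival as in the Day 30 mortality analysis (SAP 2.1), where it counts as death.
- Present a Day 59 version as supportive only, with a stated rule for days after last contact. Follow-up spans Days 52–59, may be earlier for clinical failures who stop study drug before Day 22 (SAP 1.2), and may be refused by withdrawn subjects (Protocol 7.4.1). The Day 59 version does give credit for rescued patients who leave hospital after Day 30.
- Keep the existing stay tables, labelled as conditional on not dying before discharge.
- Reconcile the condition with Protocol 13.6 and SAP 2.4, and list it in SAP section 6.

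The cost is one more derived variable for each setting, built from admission, discharge and death dates that the SAP already uses, and a few lines of text. The downside is a composite that mixes mortality with bed use and has to be explained.

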6.1.3 End of Treatment Visit and Follow-up Visits

Subjects will complete an EOT visit within 2 calendar days after the last dose of study drug, and a Follow-up visit within the Day 52–59 period. Subjects who stop study drug prior to Day 22 AND are considered clinical failures (i.e., require a change in antifungal therapy to treat candidemia and/or invasive candidiasis) may have their Follow-up visit earlier, but the visit must still be ≥ 30 days following the last once weekly infusion of Rezafungin for Injection/placebo (i.e., Day 1, Day 8, Day 15, or Day 22).

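### SAP 4.4 turns a missing hospital discharge date into a completed stay, merging subjects still in hospital at early exit (stay cut short) with discharged subjects whose date was not recorded (stay lengthened)

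*SAP*

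**What the plan says.** Protocol 10.3 lists health economics variables among the exploratory outcomes: "These include total length of hospital stay and length of ICU stay". Protocol 13.6 plans descriptive statistics by treatment group and gives no rule there for a missing discharge date.

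SAP 4.4 supplies the rule. For subjects with a "missing hospital discharge date, the end of study date or the ICU discharge date, whichever is later, will be used for the discharge date". Three nearby sentences matter:

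- Who is summarised: "for those subjects who did not die before hospital/ICU discharge, the total number of days in hospital, in ICU, and in general ward". Subjects who die before discharge are left out.
- What is measured: "The total number of days in hospital is defined as the total number of days in hospital during the study period". Separately, "the longest length of stay for each subject will be summarized using descriptive statistics".
- Re-admission is reported for mITT subjects "who were discharged from hospital, where the initial discharge date was on or after Study Day 1". The text does not say whether an imputed discharge counts.

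Section 4.4 has no censoring, no flag or count of imputed dates, and no sensitivity analysis. Elsewhere the SAP does censor: 3.2 assigns Kaplan-Meier methods to time-to-event data, 2.3.2 censors survival time for subjects lost to follow-up, and 2.3.3 does so for time to negative blood culture.

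**The concern.** A survivor still in hospital on leaving the study has a stay known only to exceed the observed time. The rule records it as ending that day. The ICU alternative does not help when ICU discharge came before exit, because the later date is used.

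The exit day also differs between subjects in ways tied to outcome. Most finish on Day 52–59. Clinical failures who stop study drug before Day 22 "may have their Follow-up visit earlier, but the visit must still be ≥ 30 days following" the last weekly infusion (Protocol 6.1.3). Withdrawn subjects may decline the Follow-up visit (Protocol 7.4.1). With day counting from first dose, a subject who withdraws in hospital on Day 10 is scored as 10 − 1 + 1 = 10 days, which reads as a short stay.

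The same rule covers a different situation: the subject went home but the date was not recorded. There the end-of-study date is too late. The two groups carry opposite errors and a reader of the table cannot tell them apart.

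There is also a possible mismatch with the primary analysis. A subject of unknown Day 30 survival status counts as deceased for all-cause mortality (Protocol 10.1), yet nothing in SAP 4.4 stops that subject from entering the stay summary as discharged alive.

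**Working it through.** The plan states no length-of-stay figure, so there is nothing to reproduce.

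**From the documents.** The imputation rule, the exclusion of deaths before discharge, and day counting from first dose (SAP 4.4). The earliest Follow-up visit for a qualifying clinical failure is the last weekly infusion day plus 30: 1 + 30 = Day 31, 8 + 30 = Day 38, 15 + 30 = Day 45 (Protocol 6.1.3). SAP 4.4 does not define the end of study date; I read it as each subject's own exit date.

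**Assumed.** Survivors only; memoryless stay in whole days with mean M = 15, 25 or 40; early exit on a day spread evenly over Days 3–28 for a share q of subjects; everyone else followed to Day 59; exit unrelated to stay.

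**Step 1: recorded mean when observation stops at Day T.**

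f(T) = (1 − e^(−T/M)) / (1 − e^(−1/M))

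For M = 25 the denominator is 1 − e^(−0.04) = 0.0392.
- f(59) = 0.9056 / 0.0392 = 23.1 days. This is the true mean capped at Day 59.
- Averaged over T = 3 to 28, e^(−T/25) is 0.562, so the mean of f(T) is 0.438 / 0.0392 = 11.2 days.

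**Step 2: two arms, identical true stays, no unrecorded dates.** The recorded mean is f(59) − q × [f(59) − mean f(T)]. For M = 25 this is 23.1 − 11.9q, which gives 22.5 at q = 5% and 21.3 at q = 15%. The gap is 0.10 × 11.9 = 1.2 days.

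| Mean stay M | Capped at Day 59 | Mean f(T), Days 3–28 | Early exits still in hospital | Recorded, q = 5% | Recorded, q = 15% | Gap |
|---|---|---|---|---|---|---|
| 15 | 15.2 | 9.3 | 40% | 14.9 | 14.3 | 0.6 |
| 25 | 23.1 | 11.2 | 56% | 22.5 | 21.3 | 1.2 |
| 40 | 31.2 | 12.5 | 69% | 30.3 | 28.4 | 1.9 |

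Only exits that occur in hospital cause the loss: at M = 25 these are about 0.05 × 56% = 3% versus 0.15 × 56% = 8% of subjects. Lognormal stays (log-scale SD 0.8) give gaps of 0.5, 1.1 and 1.9 days.

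**Step 3: later exits cost less.** At M = 25 the average shortfall per exiting subject, f(59) − f(T), is 23.1 − 18.1 = 5.0 days at Day 31, 3.2 at Day 38 and 1.8 at Day 45. A Day 10 withdrawal costs 14.7.

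**Step 4: the opposite error.** Suppose a share u of discharged subjects has no recorded date, with q = 15%. The mean exit day is 0.85 × 59 + 0.15 × 15.5 = 52.5. The recorded mean rises by u × (52.5 − recorded mean).
- M = 25: 21.3 + 0.05 × 31.2 = 22.9, and 21.3 + 0.10 × 31.2 = 24.4, against a true 23.1. The sign turns at about (23.1 − 21.3) / 31.2 ≈ 6%.
- M = 15: 14.3 + 0.05 × 38.2 = 16.2, against a true 15.2.
- M = 40: 28.4 + 0.10 × 24.0 = 30.8, against a true 31.2, so still low.

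**Step 5: scale against sampling error.** At M = 25 the second moment of the capped stay is the sum over t = 0 to 58 of (2t + 1)e^(−t/25), which gives an SD of about 18.4 days. With at most 92 per arm, the standard error of a difference is at least 18.4 × √(2/92) = 2.7 days.

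**The case against.** The case for leaving the rule alone is substantial, and much of it stands.

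- **Definition.** Total days are defined as days within the study period. For a completer still in hospital at Day 52–59, stopping there gives exactly that quantity. A reader might infer that every subject still in hospital is understated, completers included; for total days the documents do not support this. Only unequal exit times are at issue.
- **Direction.** A reader might infer that the arm with more early exits will show shorter stays, or that both arms are understated. Neither follows. Deaths before discharge are excluded, exits after a recorded discharge are unaffected, and unrecorded dates push the other way (step 4). The rule can pull an arm below its own truth without making it shorter than the other arm.
- **Reach.** The imputation sentence follows the total-days definition. That it also feeds the longest-stay summary, which covers "the time to discharge for each admission to hospital and to ICU will be generated and the longest length of stay for each subject", is a natural reading but is not stated. Nor do the documents say that imputed discharges enter the re-admission denominator, so dilution of that percentage is a possibility to close off, not a stated effect.
- **Early Follow-up.** It is optional and limited to clinical failures; Day 31 requires that the last weekly infusion was Day 1.
- **Stakes.** The comparison is untested, admissions are listed by subject, and the 1.2-day artefact at M = 25 is less than half a standard error.

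What remains is that a censored stay is scored as completed, without a flag, under a rule that mixes two opposite errors.

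**Conclusion.** The point holds as a cheap improvement. SAP 4.4 treats a missing hospital discharge date as a discharge. For survivors who exit early while in hospital this can understate stay, more in an arm with more such exits. For discharged subjects with an unrecorded date it overstates stay. The net direction cannot be determined from the documents.

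The artefact is about 0.5 to 2 days between arms with identical true stays. That size rests entirely on assumed stays, on 5% versus 15% early exits during Days 3–28, on no unrecorded dates, and on exit being unrelated to stay. No test, primary endpoint or primary conclusion depends on it.

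**What to change.** In SAP 4.4, stop treating the imputed date as a discharge:

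1. Censor survivors with no discharge by study exit at the last date known to be in hospital, or at study exit if that date is not captured.
2. Summarise time to discharge by the cumulative incidence of live discharge, with death as a competing event, through a common day such as Day 52.
3. Report by arm the number still hospitalised at exit and, separately, the number discharged with an unrecorded date. Do not assign the latter the exit date.
4. Count only observed discharges in the re-admission denominator.

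The cost is a paragraph in the SAP and re-programming of one set of descriptive tables. It should need no new data, although the case report form is not available to confirm that a last in-hospital date is recorded.

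Two downsides remain. Stay is reported as a cumulative incidence or median instead of a simple mean. Censoring at early exit still assumes that exit is unrelated to remaining stay, which is doubtful for clinical failures, so the counts in item 3 should be shown beside the curves.

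### SAP 4.4 divides Day 30 hospital re-admission and ICU re-admission by subjects who could not have had the event, so both percentages come out too low by an unknown amount

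*SAP*

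**What the plan says.** SAP 4.4 (Analysis of Health Outcomes) gives the number and percentage of subjects re-admitted to hospital and to ICU "after discharge by Day 30 (-2 days) and by Follow-up (Days 52-59) will be presented by treatment group". One denominator serves both outcomes and both time points: "for all subjects in the mITT population who were discharged from hospital, where the initial discharge date was on or after Study Day 1". It has a lower limit on discharge date and no upper limit. For the ICU, the event counted is being "re-admitted to ICU during initial hospitalization", yet the denominator stays the hospital-discharged group. The analysis is repeated for re-admissions related to infectious disease and to candidiasis.

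Four other places bear on this:

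- SAP 2.4 defines the outcome without any at-risk restriction and names only the mITT population: "will be presented by treatment group in the mITT population for all re-admissions".
- SAP 4.4 expects subjects who were never in an ICU: "the number and the percentage of the subjects with no ICU admission, 1 ICU admission, and 2 ICU admissions will be presented".
- Time to re-admission is descriptive: "Descriptive statistics will be used to summarize the time to first re-admission from the previous discharge date". No censoring, person-time or competing-risk method is given.
- The general rule in SAP 3.2 reduces denominators for missing data. It does not remove subjects who are not at risk.

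**The concern.** A re-admission percentage is interpretable only if everyone in the denominator could have had the event. Here, three groups are misplaced.

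1. Subjects first discharged after Day 30 had no time at risk by Day 30. They enter the Day 30 denominator as non-events.
2. Subjects never in an ICU cannot return to one. They enter the ICU denominator as non-events.
3. Subjects who left the ICU, went back during the initial hospitalization and then died in hospital were never discharged from hospital, on the natural reading. They drop out of the ICU rate altogether, although they are its most serious cases.

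Time at risk also varies among those discharged by Day 30, from 29 days for discharge on Day 1 to none for discharge on Day 30, and nothing adjusts for it. The reported levels would therefore be too low. If the arms differed in discharge timing, the between-arm comparison of hospital re-admission could be distorted as well.

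**Working it through.** **Inputs.** The denominator and time points are those of SAP 4.4. The documents give no re-admission rate, discharge-time distribution or ICU share, so there is no plan figure to reproduce. Every number below rests on a stated assumption.

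**1. Day 30 hospital re-admission.** Let r be the proportion re-admitted by Day 30 among subjects discharged by Day 30, and L the share of the denominator discharged later. Late discharges contribute no events, so

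reported rate = r × (1 − L).

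Example: 60 subjects are discharged by Day 30, 20 later, and 9 are re-admitted by Day 30. Then r = 9/60 = 15%, L = 20/80 = 25%, and the reported rate is 9/80 = 11.25% = 15% × 0.75.

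| L (assumed) | 10% | 20% | 30% | 40% |
|---|---|---|---|---|
| Reported when r = 15% | 13.5% | 12.0% | 10.5% | 9.0% |

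**2. ICU re-admission.** Let q be the re-admission proportion among ICU-discharged subjects in the denominator, and S their share of that denominator. Then

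reported rate = q × S.

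| S (assumed) | 20% | 40% | 60% | 80% |
|---|---|---|---|---|
| Reported when q = 10% | 2% | 4% | 6% | 8% |

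The loss of subjects who returned to the ICU and died in hospital is a separate effect and is not in this formula.

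**3. Comparison between arms, hospital re-admission.** Assume Weibull time to discharge (shape 1.5), discharges counted to Day 55, and the same post-discharge hazard h per day in both arms. A subject discharged on day t ≤ 30 is re-admitted by Day 30 with probability 1 − exp(−h(30 − t)). With h = 0.01:

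| Median discharge day | L | Day 30, as written | Day 30, discharged by Day 30 only | By Day 55 |
|---|---|---|---|---|
| 14 | 11.0% | 13.1% | 14.7% | 31.6% |
| 21 | 26.7% | 9.5% | 12.9% | 27.2% |
| 28 | 37.0% | 7.6% | 12.1% | 24.5% |

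For medians of 14 v 21 days the artificial gap is 13.1 − 9.5 = 3.6 points as written, and 14.7 − 12.9 = 1.8 points with the restricted denominator. With equal medians the gap is 0.

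Over h = 0.005, 0.01 and 0.02 and the pairs 14/21, 14/28 and 21/28, the gaps are:

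- Day 30 as written: 1.0 to 9.8 points
- Day 30 restricted: 0.4 to 4.5 points
- Follow-up: 1.5 to 10.8 points

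Restricting the denominator therefore removes only about half of the gap.

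**4. A second assumed distribution.** A simulation with gamma time to discharge (shape 1.5), discharge by Day 59 and hazard 0.008 per day gives:

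| Median discharge day | 12 | 16 | 20 | 24 |
|---|---|---|---|---|
| As written | 12.0% | 10.0% | 8.6% | 7.7% |
| Discharged by Day 30 only | 13.4% | 12.4% | 11.7% | 11.2% |

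For 16 v 20 days the gap is 1.4 points as written and 0.7 points restricted. Re-admissions per 1000 days out of hospital are 8.0 at every median, so a person-time rate does not have the artefact.

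**The case against.** The strongest reply concerns consequence, not wording. A reader might infer that a once-weekly drug lets patients leave earlier than daily infusions do, so that this table would turn a real benefit into apparent harm. The documents do not support that. Under the double-dummy design (Protocol 6.3), both arms receive daily infusions until step-down, then daily oral therapy with weekly infusions. Step-down and outpatient IV rules are the same in both arms. Dosing convenience is masked and gives no reason to expect different discharge times. A difference could still arise through efficacy or safety, but without one the denominator lowers both arms alike and creates no gap. Nor does any faster-arm-looks-worse reading carry over to the ICU rate, whose dilution depends on each arm's ICU share.

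The table also carries little weight. Health-economic variables are exploratory (Protocol 10.3), and Protocol 13.6 plans only descriptive length of stay. SAP 4.4 attaches no test or interval to re-admission. Under the gamma assumption with medians of 16 v 20 days, the gap of 1.4 points is 92 × 0.014 = 1.3 subjects per arm, even if all 92 were discharged. The standard error of the difference would be about √(2 × 0.093 × 0.907 / 92) = 4.3 points. SAP 4.4 also reports length of stay, counts of ICU admissions and by-subject listings, so a careful reader could see different discharge timing and approximate repeat ICU admission.

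All of this stands on importance. It does not correct the denominators: the printed percentages would still include subjects not at risk, and the adjacent tables let a reader approximate the right figure without replacing it. The further point that restricting to subjects discharged by Day 30 conditions on a post-randomization event is fair, and is one more reason not to rely on the restriction alone.

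**Conclusion.** The concern holds for the denominators and is of low priority. As written, the Day 30 hospital re-admission percentage is understated by exactly the share of the denominator discharged after Day 30. The ICU percentage is diluted by the share never discharged from an ICU, and on the natural reading it omits subjects who returned to the ICU and then died in hospital. Neither share can be determined from the documents. A distorted comparison is conditional: only if the arms differ in discharge timing while post-discharge risk is similar would the earlier-discharging arm show the higher hospital re-admission percentage. No primary or secondary efficacy conclusion depends on this table.

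One point adds uncertainty. SAP 4.4 imputes discharge dates for length of stay: "For the subjects with missing hospital discharge date, the end of study date or the ICU discharge date, whichever is later". If that rule were also applied here, subjects with no recorded discharge would enter the denominator as late discharges.

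**What to change.** In SAP 4.4:

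- **Hospital re-admission by Day 30:** use as denominator mITT subjects discharged alive on or after Study Day 1 and by Day 30.
- **ICU re-admission during the initial hospitalization:** use subjects discharged alive from an ICU on or after Study Day 1 and by the time point, whether or not they later left hospital alive.
- **Hospital re-admission at Day 30 and Follow-up:** add cumulative incidence from discharge with death as a competing event, or re-admissions per 1000 days out of hospital. The restriction alone does not remove the time-at-risk difference, and the Follow-up percentage has the same problem.
- **Missing discharge dates:** state whether the length-of-stay imputation applies to re-admission.

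Apply the same wording to the infectious-disease and candidiasis repeats, and align SAP 2.4 with it. SAP 4.4 already uses admission and discharge dates, so the cost is a wording change, a little extra programming and smaller denominators.
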